## Final Protocol

### Bangladesh PRODUCTIVity in Eyecare (B-PRODUCTIVE) Trial

**Sponsor:** Orbis

**Collaborators:** Digital Diagnostics Inc. and Deep Eye Care Foundation (DECF)

**Study Aim:** To assess the impact of using autonomous artificial intelligence (AI) for identification of diabetic retinopathy (DR) and diabetic macular edema on productivity of retina specialists in Bangladesh.

**Hypothesis:** Autonomous AI increases retina specialist productivity

**Main Study Question:** Will retina specialists complete a greater number of diabetic eye exams per working hour (including persons reviewed by AI whom the retina specialist does not need to see personally) when they use autonomous AI in a randomized clinical trial?

**Design:** Cluster-randomized (by clinic day) controlled trial.

**Randomization:** By clinic day. Each morning the clinic manager will be notified if it is an Intervention (AI) or Control (non-AI) day.

**Interventions:** All patients in both groups go through the eligibility checklist. If approved, they will be evaluated by autonomous AI. This is done to decrease potential bias (neither patients nor physicians know the group assignment of participants) and concealment (so that neither patients nor doctors can arrange visits on a known "Intervention Day").

**Intervention Group:** On randomly selected "Intervention" clinic days, if patients screen positive or have insufficient image quality, they continue to the retina specialist. If not eligible for autonomous AI, they proceed straight to the retina specialist without autonomous AI evaluation. If patients receive a negative result, they do not see the retina specialist, and are referred for a visit at the regular eye clinic (not the retina clinic) in 3 months.

**Control Group:** On randomly-selected "Control Days," all patients see the retina specialist, irrespective of the results of autonomous AI evaluation.

**Masking:** The retina doctors are masked both patient group assignment (that is, whether autonomous AI was used for pre-screening or not on the particular clinic day)

and also masked to the results of the AI on Intervention days. Patients are also masked to group assignment and autonomous AI results.

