### 2. Outcome Measures

#### 2.1. Main Study Outcome:

The number of examined patients with diabetes per retina specialist working hour between AI and non-AI days.

- Numerator: number of examined patients
  - Sum of the number of patients diagnosed with diabetes mellitus (type 1 or type 2) examined for DR per day
  - Patients included have not been previously diagnosed with DR
  - Includes all patients evaluated by autonomous AI on AI days, even if they are not seen by the retina specialist
- Denominator: retina specialist working time (hours)
  - Sum of retina specialist time spent on all diabetes patients examined per day
  - Does not include patient time spent during autonomous AI evaluation
  - Excluding treatment or surgical time
  - Including retina specialist time spent on ordering & reviewing diagnostic studies and scheduling treatment/surgery

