## 4. Sample Size Calculations

The null hypothesis is that diabetic patients without known DR seen by retina specialist per doctor hour for regular clinic days and AI days are the same. We are estimating the sample size needed to reject this null hypothesis. In calculating the sample size we used 80% power (the probability of rejecting a false null hypothesis). The sample size estimate is 924 patient participants.

Inputs for the sample size estimate calculations are:

- 80% power; power is the probability of rejecting a false null hypothesis.
- Alpha of 5%; probability of rejecting a true null hypothesis.
- Average cluster size of 8 and cluster size coefficient of variation of 0.45 (based on March data).
- Mean number of diabetic patients without known DR seen per doctor hour is 1.34 (based on Quarter 1 data). Hospital records that were used to calculate the sample size show that there are approximately 366 diabetic patients seen at the hospital per month. The retina clinic examines approximately 237 patients with diabetes per month.
- We changed some factors, but decided on one estimate.

Mean of Group 1	Mean of Group 2	Mean Difference	Intra-cluster correlation coefficient	Sample Size estimate
-----------------	-----------------	-----------------	---------------------------------------	----------------------

1.34	1.68	0.34	0.15	924
------	------	------	------	-----

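### The clinic manager is told the arm each morning while concealment covers only patients and doctors; differential same-day routing or enrolment, if it occurred, would favour the AI arm

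*Combined protocol and SAP*

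**What the plan says.** The protocol, under Randomization, states: "Each morning the clinic manager will be notified if it is an Intervention (AI) or Control (non-AI) day". Under Interventions it says that "All patients in both groups go through the eligibility checklist" and that those approved are evaluated by AI on both kinds of day. One stated reason is concealment, "so that neither patients nor doctors can arrange visits on a known" intervention day. The masking paragraphs of the protocol and SAP section 5 cover retina doctors and patients. No other role is mentioned.

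SAP 2.1 defines the primary numerator as "Sum of the number of patients diagnosed with diabetes mellitus (type 1 or type 2) examined for DR per day" and adds: "Includes all patients evaluated by autonomous AI on AI days, even if they are not seen by the retina specialist". The denominator is "Sum of retina specialist time spent on all diabetes patients examined per day", with the rule: "Does not include patient time spent during autonomous AI evaluation".

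SAP section 4 gives an average cluster size of 8, a current rate of 1.34 per doctor hour and a planned AI-day rate of 1.68. It also reports "approximately 366 diabetic patients seen at the hospital per month" and about 237 diabetes patients per month examined in the retina clinic.

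**The concern.** The plan recognises that advance knowledge of the arm could change who attends, and it guards against this for patients and doctors. The one role it names as knowing the arm at the start of the day is clinic management. The arm is needed only when an AI result is acted on, so the early notice to the manager serves no purpose that the documents state.

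The primary outcome makes this matter more than it would in most cluster trials. Part of the numerator on AI days is a count of patients who use no specialist time. Whoever influences how many diabetes patients are sent to the retina clinic that day, or are offered AI, can influence the outcome directly. It need not be deliberate: a little more effort to find eligible patients on AI days would be enough. The same effort on control days would leave the rate about where it was, so the error would run in one direction.

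**Working it through.** **Inputs from SAP section 4:** cluster size 8, taken as diabetes patients per clinic day; control rate 1.34 per hour, taken to have the denominator of SAP 2.1; AI-day rate 1.68; 366 and 237 diabetes patients per month.

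**Assumptions not in the documents:** 22 to 26 clinic days per month; a chance of 0.5 to 0.8 that an extra patient is AI-negative; an extra patient who does see the specialist takes the average time, 1/1.34 = 0.746 h.

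**Plan's own figures.** The planned difference reproduces: 1.68 − 1.34 = 0.34. The total of 924 cannot be reproduced from the stated inputs because no standard deviation is given. With the design effect 1 + ((1 + 0.45²) × 8 − 1) × 0.15 = 2.293 and a two-sided 5% test, a Poisson-type variance of 1.51 gives 946. Exactly 924 implies a standard deviation of about 1.22. Nothing below depends on this.

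**Illustration, starting from an AI day with no true effect**

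1. Specialist time per clinic day: 8 / 1.34 = 5.970 h.
2. One extra AI-negative patient on an AI day: (8 + 1) / 5.970 = 1.5075, a rise of 0.1675 per hour.
3. Share of the planned effect: 0.1675 / 0.34 = 49%.
4. Extra AI-negative patients per AI day that would equal the whole planned effect: 0.34 × 5.970 = 2.03.
5. One extra patient on a control day: 9 / (5.970 + 0.746) = 1.34, unchanged.
6. One patient removed from a control day: 7 / (5.970 − 0.746) = 1.34, unchanged.

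**Sensitivity, one assumption changed at a time**

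| Change | Formula | Rise per hour | Share of 0.34 |
|---|---|---|---|
| Chance of AI-negative 0.8 | 9 / (5.970 + 0.2 × 0.746) − 1.34 | 0.131 | 38% |
| Chance of AI-negative 0.6 | 9 / (5.970 + 0.4 × 0.746) − 1.34 | 0.096 | 28% |
| Chance of AI-negative 0.5 | 9 / (5.970 + 0.5 × 0.746) − 1.34 | 0.079 | 23% |
| Half of AI days gain one | 0.5 × 0.1675 | 0.084 | 25% |
| A quarter of AI days gain one | 0.25 × 0.1675 | 0.042 | 12% |
| Cluster size 12 | 1.34 / 12 | 0.112 | 33% |
| Cluster size 10 | 1.34 / 10 | 0.134 | 39% |
| Cluster size 6 | 1.34 / 6 | 0.223 | 66% |
| 8 is the AI-day mean at 1.68 per hour | 1.68 / 8 | 0.210 | 62% |

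Reductions combine. With a chance of 0.5 and half of AI days affected, the rise is 0.5 × 0.079 = 0.039, or 12%. With a quarter of AI days it is 0.020, or 6%.

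**Size of the pool.** 366 − 237 = 129 diabetes patients per month seen elsewhere in the hospital: 129 / 26 = 5.0 to 129 / 22 = 5.9 per clinic day. This is an upper limit. SAP 2.1 excludes patients already diagnosed with DR, and the protocol's criteria for AI participants add limits on age, visual acuity, symptoms and earlier retinal treatment. The documents do not say how many of the 129 would pass.

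**The case against.** The strongest reply is that the mechanism is inferred. No section gives the manager a part in registration, routing, the checklist or consent. SAP section 5 makes consent a condition of eligibility but does not time it, and its timing may be set out in consent material outside these two documents. That stands: the documents do not establish that screening and consent follow the notice, although a morning notice and a checklist leading to AI evaluation make it the natural reading.

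A reader might go further and infer that patients are being steered into AI days, or that half the planned effect is likely to be artefact. The documents support neither. They show only that nothing prevents it, and 49% needs an extra eligible, consenting, gradable, AI-negative patient on every AI day.

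The plan also has real safeguards. Same-morning notice limits advance booking, and running AI on both kinds of day protects against patients and doctors. The daily counts in SAP 3.2 and the cluster flow diagram in SAP 6.1 could partly reveal an imbalance. They would do so afterwards and prevent nothing. SAP 6.2 lists completed specialist visits, which leave out the AI-negative patients on AI days.

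Finally, if AI frees capacity and the clinic then takes more diabetes patients, some extra volume may be part of the effect under study. That is fair, and it is why not all extra volume should be called bias. As written, though, the plan cannot tell volume drawn in by freed capacity from volume drawn in because someone knew the arm.

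**Conclusion.** The concern holds as a preventable risk of bias. The protocol discloses the arm to the clinic manager each morning, its concealment reaches only patients and doctors, and the primary outcome rewards extra AI-negative inflow on AI days alone. One such patient on every AI day would add 0.17 per hour, 49% of the planned effect, assuming 8 diabetes patients per day, 1.34 per hour on the SAP 2.1 denominator, and no specialist time for that patient. Changing one assumption at a time gives about 12% to 66%; combinations of the milder assumptions go lower.

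Three things are not established: that the manager influences patient flow, that consent follows the notice, and that the 129 patients per month are available or eligible. The change is worth making because it is cheap and the possible error favours the trial's hypothesis.

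**What to change.** **Protocol, Randomization.** State that the day's arm is not released to the clinic manager or to anyone who registers, routes, screens, consents or images patients. Release it to one existing staff member outside those steps, who applies it to each patient only after consent and after the AI result, including image sufficiency, has been recorded. The AI operator should not hold it: an operator who knew the arm could affect image sufficiency for later patients, and image sufficiency decides who goes on to the specialist on AI days.

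**SAP 6.2.** Add a table by arm and per clinic day of diabetes patients registered, eligible, consented and with insufficient images. An imbalance would then be visible, whatever its cause.

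**Cost.** A wording change, a different recipient and time of release for the allocation, and one more table. Sample size and primary analysis are unaffected. The protocol gives an actual start date, so this may be an amendment to a running trial; days before and after the change should then be identified. Staff may still infer the arm after the first AI-negative discharge of the day, so concealment would be better but not complete, and the table covers what remains.

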## **Study Design**

**Study Type:** Interventional (Clinical Trial)

**Estimated Enrollment:** 924 participants

**Allocation:** Randomized

**Intervention Model:** Parallel Assignment

**Intervention Model Description:** Cluster-randomized (by clinic day) controlled trial.

**Masking:** Double (Participant, Patient)

**Masking Description:** The retina specialists are masked both to patient group assignment (that is, whether autonomous AI results were used or not on the particular clinic day) and also masked to the results of the autonomous AI on Intervention days. Patients are also masked to group assignment and autonomous AI screening results.

**Primary Purpose:** Diagnostic

**Official Title:** Assessing the Impact of Using Autonomous Artificial Intelligence (AI) for Pre-screening of Diabetic Retinopathy (DR) and Diabetic Macular Edema on Physician Productivity in Bangladesh

**Actual Study Start Date:** March 20, 2022

**Estimated Primary Completion Date:** December 2022

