## **Arms and Interventions**

Arm	Intervention
Experimental: Intervention group  Autonomous AI results are used to evaluate if the participant needs to see the retina specialist (positive result0 or not (negative result).	Diagnostic test: results utilized from autonomous AI diagnostic system for diabetic retinopathy and/or diabetic macular edema.  If patients receive a negative result they do not see the retina specialist
No Intervention: Control group	

All participants see the retina specialist irrespective of the results of their autonomous AI evaluation.

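### Does it undermine the claimed masking that some patients, and perhaps specialists, can infer the day type from the triage route?

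*Combined protocol and SAP*

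**What the plan says.** The protocol's Masking paragraph says "Patients are also masked to group assignment and autonomous AI results". The Masking Description under Study Design repeats it: "Patients are also masked to group assignment and autonomous AI screening results". SAP section 5 says the same, and none of the three gives an exception. Specialists are also said to be masked to the day type and to the AI results on Intervention days.

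The routes differ by day. On Intervention days, "If patients receive a negative result, they do not see the retina specialist, and are referred for a visit at the regular eye clinic"; the Arms and Interventions table agrees: "If patients receive a negative result they do not see the retina specialist". Patients with a positive result or inadequate images go on to the specialist. On Control days, "all patients see the retina specialist, irrespective of the results of autonomous AI evaluation".

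The masking label under Study Design is "Double (Participant, Patient".

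For the main outcome (SAP 2.1), the numerator "Includes all patients evaluated by autonomous AI on AI days, even if they are not seen by the retina specialist", and the denominator is the "Sum of retina specialist time spent on all diabetes patients examined per day". Patient satisfaction with AI is a secondary outcome (SAP 2.2.3). SAP 3.2 places its survey after the AI examination but does not say whether the patient by then knows the next step.

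**The concern.** A statement that all patients are masked to group and result conflicts with a pathway that sends one identifiable set of them away early. If those patients know why, the trial is not masked for them, and their satisfaction answers may reflect that knowledge.

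The more serious worry is the specialist. Specialist time is the denominator of the main outcome. A specialist who sensed an AI day from a short list could work faster or slower, and the rate would then reflect belief as well as triage. SAP 3.1.2 plans masked recording of physician time, which protects the measurement but not the pace of work. No check of masking or of pace is planned.

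The label also seems to name one party twice and to omit the specialist.

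**Working it through.** **Patients.** The routes of AI-evaluated patients, side by side:

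| Day | AI result | Sees the specialist? |
|---|---|---|
| Intervention | Negative | No |
| Intervention | Positive or insufficient image | Yes |
| Control | Any | Yes |

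Only one row ends without a specialist visit, so a patient in that row who knows the rule can be certain of day and result. Patients who are seen remain uncertain. With equal numbers of each type of day and an AI-negative share p (both assumptions; the documents give no p), the chance that a seen patient came on an Intervention day is (1 − p)/(2 − p): 0.33 at p = 0.5 and 0.09 at p = 0.9.

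For the main rate, an AI-negative Intervention-day patient adds one to the numerator and no specialist time, whatever he or she has inferred.

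**Label.** The 924 participants under Study Design are patients, which makes the label look duplicated. But SAP 3.2 and 6.2 also apply the word participant to specialists, and the Masking Description names specialists and patients.

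**Specialists (illustration only).** Inputs from SAP section 4 are rates of 1.34 and 1.68, mean cluster size 8 and coefficient of variation 0.45. The assumptions are that 8 means diabetes patients per clinic day, time per seen patient is equal, there are as many AI as Control days, and daily counts are negative binomial.

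- Diverted share giving the planned rise: q = 1 − 1.34/1.68 = 0.202, or 0.202 × 8 = 1.6 patients a day, against a day-to-day SD of 0.45 × 8 = 3.6.
- Negative binomial size: 64/(3.6² − 8) = 12.9.
- Guessing an AI day when the count is more likely on an AI day (7 or fewer) gives that guess on pA = 0.676 of AI days and pC = 0.486 of Control days. It is right on (0.676 + 0.514)/2 = 0.595 of days.
- If time per patient is cut by a fraction d on days guessed to be AI days, the rate ratio is multiplied by (1 − d·pC)/(1 − d·pA).

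| d (assumed) | AI rate, 1.68/(1 − d·pA) | Control rate, 1.34/(1 − d·pC) | Difference | Change from 0.34 | Ratio multiplied by |
|---|---|---|---|---|---|
| 0.05 | 1.739 | 1.373 | 0.365 | +7.5% | 1.010 |
| 0.10 | 1.802 | 1.408 | 0.393 | +15.7% | 1.020 |
| −0.05 | 1.625 | 1.308 | 0.317 | −6.8% | 0.991 |
| −0.10 | 1.574 | 1.278 | 0.296 | −13.0% | 0.982 |

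Much of the change in the difference is a shift common to both arms, since Control days are also guessed to be AI days. The relative effect moves by only 1% to 2%.

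At q = 0.50 (assumption), pA = 0.766 and pC = 0.260. The guess is right on 0.753 of days, and the multiplier is 0.987/0.9617 = 1.026 at d = 0.05 and 0.974/0.9234 = 1.055 at d = 0.10. Diversion alone would then double the rate: 1/(1 − 0.50) = 2.

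**Would a supportive pace table help?** 924/8 = 115.5 days, or 57.75 per arm. The 95% half-width is 1.96 × CV × √(2/57.75), which is 7.3%, 10.9% or 14.6% for a day-level CV of minutes per patient of 0.2, 0.3 or 0.4 (assumption). The difference to be found is 1% to 2%.

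**The case for a change.** The best case for a change is that the contradiction is internal and cheap to mend. Masking is claimed three times without qualification, and the plan's own routing defeats it in one cell. An unqualified double-masking claim would misinform readers however small the bias. The survey's timing relative to routing is left open. The specialist model also counts patients only. Case mix could sharpen the cue, and the true AI-negative share could exceed 20%: with 8 AI-evaluated patients, a share of 0.5 to 0.9 leaves 4.0 to 0.8 for the specialist.

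The point about wording stands. So does the gap on survey timing, but that is detail of conduct which study staff settle and authors report. The case-mix point stands as an unquantified possibility. Against it, the model favours the cue: one observer is assumed to know the whole day's count, which is complete only at closing, whereas three specialists are named (SAP section 5) and patients without diabetes are left out. A stronger volume cue also needs more diversion, and so comes with a larger direct effect of triage.

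A pace table from daily totals would not settle the matter. SAP 2.1 excludes treatment and surgical time from the diabetes denominator, but SAP 2.2.1 states no such exclusion for all patients. Subtracting one from the other could assign treatment or idle time to patients without diabetes. A pace change prompted by a shorter list may also be part of the real effect of AI triage.

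**Conclusion.** The masking statements are broader than the pathway allows, but nothing in the design, the analysis or the main result turns on this. Withholding the specialist visit is the intervention, so its visibility to the patients concerned is a fair trade-off. Rewording the statements would leave bias, power and the main rate as they are. The label is at most a clerical slip. A reader of the plan can see which patients may infer their status, and authors can say so when they report masking and satisfaction.

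Specialist inference remains possible but unshown. The shift of 1% to 2% in the rate ratio rests on 20% diversion, a 5% to 10% change in time per patient on guessed AI days, equal time per patient and guessing from the count alone. It illustrates scale and is not an estimate for this trial. What patients are told about the triage rule cannot be judged, because consent pages are not in the review copy. No change is called for.

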## **Study Design**

**Study Type:** Interventional (Clinical Trial)

**Estimated Enrollment:** 924 participants

**Allocation:** Randomized

**Intervention Model:** Parallel Assignment

**Intervention Model Description:** Cluster-randomized (by clinic day) controlled trial.

**Masking:** Double (Participant, Patient)

**Masking Description:** The retina specialists are masked both to patient group assignment (that is, whether autonomous AI results were used or not on the particular clinic day) and also masked to the results of the autonomous AI on Intervention days. Patients are also masked to group assignment and autonomous AI screening results.

**Primary Purpose:** Diagnostic

**Official Title:** Assessing the Impact of Using Autonomous Artificial Intelligence (AI) for Pre-screening of Diabetic Retinopathy (DR) and Diabetic Macular Edema on Physician Productivity in Bangladesh

**Actual Study Start Date:** March 20, 2022

**Estimated Primary Completion Date:** December 2022

## **Arms and Interventions**

Arm	Intervention
Experimental: Intervention group  Autonomous AI results are used to evaluate if the participant needs to see the retina specialist (positive result0 or not (negative result).	Diagnostic test: results utilized from autonomous AI diagnostic system for diabetic retinopathy and/or diabetic macular edema.  If patients receive a negative result they do not see the retina specialist
No Intervention: Control group	

All participants see the retina specialist irrespective of the results of their autonomous AI evaluation.

